#### **10.4.2 Serious adverse events waived from expedited regulatory reporting to regulatory authorities**

Not applicable.

#### **10.4.3 General guidelines for reporting adverse events**

- All AEs, regardless of seriousness or relationship to IMP, spanning from the signature of the informed consent form until the end of the study as defined by the protocol for that patient, are to be recorded on the corresponding page(s) or screen(s) of the eCRF.

- Whenever possible, diagnosis or single syndrome should be reported instead of symptoms. The Investigator should specify the date of onset, intensity, action taken with respect to IMP, corrective treatment/therapy given, additional investigations performed, outcome, and his/her opinion as to whether there is a reasonable possibility that the AE was caused by the IMP or by the study procedure(s).
- The Investigator should take appropriate measures to follow all AEs until clinical recovery is complete and laboratory results have returned to normal, or until progression has been stabilized, or until death, in order to ensure the safety of the patients. This may imply that observations will continue beyond the last planned visit per protocol, and that additional investigations may be requested by the monitoring team up to as noticed by the Sponsor.
- When treatment is prematurely discontinued, the patient's observations will continue until the end of the study as defined by the protocol for that patient.
- Laboratory, vital signs or ECG abnormalities are to be recorded as AEs only if:
  - Symptomatic and/or
  - Requiring either corrective treatment or consultation, and/or
  - Leading to IMP discontinuation or modification of dosing, and/or
  - Fulfilling a seriousness criterion, and/or
  - Defined as an AESI.

Instructions for AE reporting are summarized in Table 1.

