## 6 STUDY DESIGN

### 6.1 DESCRIPTION OF THE STUDY

This is a national, multicenter, open-label, single-arm phase IV study designed to assess the effect of sarilumab on patient-reported impact of disease, using the rheumatoid arthritis impact of disease (RAID) questionnaire, in patients with moderately to severely active RA and inadequate response or intolerance to current csDMARD or TNF inhibitors.

Four study periods are defined for this study:

- Screening period: within 28 days prior to study treatment start (Baseline visit, Day 1), out-patient eligibility is determined at the Screening visit. At Baseline visit, patient's inclusion in the study will be established.
- 6-month core period: patients who fulfil the enrolment criteria will start the investigational medicinal product (IMP), SC injection of sarilumab 200 mg every 2 weeks as monotherapy and/or in combination with methotrexate (MTX) or other csDMARD (at investigator's discretion) for 24 weeks. Patient visits are scheduled at Baseline, W4, W12, and W24.
- Long-term extension period: all patients who will complete the 6-month-core-period will be allowed to continue the treatment with sarilumab, every 2 weeks for a maximum of another 24 weeks or until the commercial availability of sarilumab, depending whichever comes first. Patient visits are scheduled every 12 weeks over the LTE period (at W36 and W48).
- Post-treatment follow-up: each patient will have one follow-up visit, between 2 and 4 weeks after his/her last administration of sarilumab.

Around 140 patients enrolled in 35 university hospital and general hospital centers are expected throughout mainland France.

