### **6.2.2 Determination of end of clinical trial (all patients)**

The end of the clinical trial in all participating sites is reached when the last patient last visit is completed per protocol. The last patient last visit will occur 2 to 4 weeks after the last sarilumab administration (i.e. at between Week 26 and Week 28 for patients who will not enter the LTE study and between Week 50 and Week 52 at a maximum for patients who will enter the LTE study).

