### **7.2.2 Exclusion criteria related to the current knowledge of Sanofi compound**

- E 11. Pregnant or breastfeeding woman
- E 12. Women of childbearing potential not protected by highly-effective contraceptive method(s) of birth control (as defined in the informed consent form and/or in a local protocol addendum/amendment) over the study period and for at least 3 months following the last dose of sarilumab, and/or who are unwilling or unable to be tested for pregnancy
- E 13. History of severe allergic or anaphylactic reactions to human, humanized, or murine monoclonal antibodies (or to any of the excipients associated to sarilumab)
- E 14. Immunization with a live/attenuated vaccine within 4 weeks prior to Baseline
- E 15. Stage III or IV cardiac failure according to the New York Heart Association classification
- E 16. History of previous gastrointestinal perforation or diverticulitis
- E 17. Known active current/ recurrent infections (including but not limited to active tuberculosis [TB] or history of incompletely treated TB and atypical mycobacterial disease, hepatitis B and C, and herpes zoster)  
  
NOTE: in case of latent TB infection the patient may be included if a subsequent appropriate anti TB treatment is initiated since at least 3 weeks
- E 18. Positive hepatitis B surface antigen (HbsAg), and/or positive total hepatitis B core antibody, and/or positive hepatitis C antibody (HCV) at the Screening visit
- E 19. Evidence of serious uncontrolled concomitant disease, including severe uncontrolled hypercholesterolemia or hypertriglyceridemia
- E 20. Patients with any of the following laboratory abnormalities at the Screening or Baseline visit:

- Hemoglobin <8.5 g/dL
- White blood cells <3000/mm^3
- Absolute neutrophil count <2000/mm^3
- Absolute lymphocyte count <500/mm^3
- Platelet count <150 000 cells/mm^3
- Creatinine clearance <30 mL/min
- AST or ALT >1.5 x ULN.
- Bilirubin (total) >ULN, unless Gilbert's disease has been determined by genetic testing and has been documented
- Total fasting cholesterol >3.50 g/L [9.1 mmol/L]) or triglycerides >5.00 g/L [5.6 mmol/L])

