#### **10.4.1.3 Adverse event of special interest**

An adverse event of special interest (AESI) is an AE (serious or non-serious) of scientific and medical concern specific to the Sponsor's product or program, for which ongoing monitoring and immediate notification by the Investigator to the Sponsor is required. Such events may require further investigation in order to characterize and understand them. Adverse events of special interest may be added, modified or removed during a study by protocol amendment.

Any AESIs will be reported to the Sponsor in the same timeframe as SAEs, ie, within 24 hours, as detailed in Section 10.4.5.

For this study, AESIs are defined as:

- Pregnancy of a female subject in the study
  - It will be qualified as a SAE only if it fulfills one of the seriousness criteria (see Section 10.4.1.2)
  - In the event of pregnancy in a female participant, IMP should be discontinued
  - Follow-up of the pregnancy in a female participant is mandatory until the outcome has been determined (see Appendix A).
- Symptomatic overdose (serious or non-serious) with IMP
  - An overdose (accidental or intentional) with the IMP is an event suspected by the Investigator or spontaneously notified by the patient (not based on systematic pills count) and defined as at least twice the dose during the planned intervals.

Of note, asymptomatic overdose has to be reported as a standard AE.

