#### **10.4.4 Instructions for reporting serious adverse events**

In the case of occurrence of an SAE, the Investigator or any designees must immediately:

- ENTER (within 24 hours) the information related to the SAE in the appropriate screens of the eCRF; the system will automatically send a notification to the monitoring team after approval of the Investigator within the eCRF or after a standard delay.
- SEND (preferably by fax or e-mail) a photocopy of all examinations carried out and the dates on which these examinations were performed, to the representative of the monitoring team whose name, fax number, and email address appear on the clinical trial protocol. Care should be taken to ensure that the patient's identity is protected and the patient's identifiers in the clinical trial are properly mentioned on any copy of a source document provided to the Sponsor. For laboratory results, include the laboratory normal ranges.
- All further data updates should be recorded in the eCRF as appropriate, and further documentation as well as additional information (for laboratory data, concomitant medications, patient status, etc.) should be sent (by fax or e-mail) to the monitoring team within 24 hours of knowledge of the SAE. In addition, every effort should be made to further document any SAE that is fatal or life-threatening within a week (7 days) of the initial notification.

- A back-up plan (using a paper CRF process) is available and should be used when the eCRF system does not work.

Any SAE brought to the attention of the Investigator at any time after the end of the study for the patient and considered by him/her to be caused by the IMP with a reasonable possibility, should be reported to the monitoring team.

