**Table 2: Highly Effective Contraceptive Methods**

Highly Effective Contraceptive Methods That Are User Dependenta Failure rate of <1% per year when used consistently and correctly

• Combined (estrogen- and progestogen-containing ) hormonal contraception associated with inhibition of ovulationb

- oral

- intravaginal

- transdermal

• Progestogen-only hormone contraception associated with inhibition of ovulation

- oral

- injectable

Highly Effective Methods That Are User Independenta

• Implantable progestogen-only hormonal contraception associated with inhibition of ovulationb

- Intrauterine device (IUD)

- Intrauterine hormone-releasing system (IUS)

• Bilateral tubal occlusion

Vasectomized partner A vasectomized partner is a highly effective contraceptive method provided that the partner is the sole sexual partner of the WOCBP and the absence of sperm has been confirmed. If not, an additional highly effective method of contraception should be used.
Sexual abstinence Sexual abstinence is considered a highly effective method only if defined as refraining from heterosexual intercourse during the entire period of risk associated with the study treatment. The reliability of sexual abstinence needs to be evaluated in relation to the duration of the study and the preferred and usual lifestyle of the participant.
NOTES:  a) Typical use failure rates may differ from those when used consistently and correctly. Use should be consistent with local regulations regarding the use of contraceptive methods for participants participating in clinical studies.  b) Hormonal contraception may be susceptible to interaction with the study treatment, which may reduce the efficacy of the contraceptive method. In this case TWO highly effective methods of contraception should be utilized during the treatment period and for up to 3 months after treatment after the last dose of study treatment.

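### For patients who complete treatment or stop late, there is no clear duty to report a new pregnancy for about 69% to 85% of the 3-month post-dose contraception period

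*Protocol*

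**What the plan says.** Protocol 10.4.1.3 lists "Pregnancy of a female subject in the study" as one of two adverse events of special interest (AESIs). It requires notification within 24 hours and follow-up of a known pregnancy to its outcome, and it makes a pregnancy a serious adverse event (SAE) only if a seriousness criterion is met.

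Protocol 10.4.3 sets the recording window for adverse events: "spanning from the signature of the informed consent form until the end of the study as defined by the protocol for that patient". Section 6.1 fixes the last contact: "each patient will have one follow-up visit, between 2 and 4 weeks after his/her last administration of sarilumab". Section 6.2.2 places it "at between Week 26 and Week 28 for patients who will not enter the LTE study". With the extension, it falls at Weeks 50 to 52 at the latest. The last scheduled pregnancy test is at that visit (10.1.6).

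E 12 in section 7.2.2 excludes women of childbearing potential who are not protected by highly effective contraception "over the study period and for at least 3 months following the last dose of sarilumab". A note to Table 2 in Appendix A, on using two methods where hormonal contraception may interact with study treatment, uses the same horizon: "during the treatment period and for up to 3 months after treatment after the last dose of study treatment".

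After a patient's end of study, section 10.4.4 keeps one route open, for an SAE "considered by him/her to be caused by the IMP with a reasonable possibility, should be reported". Section 10.4.5 sends AESIs to the notification procedure of 10.4.4 whether or not they are serious. Section 10.4.1.3 points to Appendix A for pregnancy follow-up. The title of that appendix promises the collection of pregnancy information, but its text contains only the definitions of childbearing potential and the contraception guidance.

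**The concern.** The protocol carries its contraception requirement to 3 months after the last dose, but its recording window for the related event closes after 2 to 4 weeks for anyone who completes treatment or stops near the end. A non-serious pregnancy that begins between that visit and the end of the contraception period has no clear reporting route. Follow-up to outcome does not help, because it applies only to a pregnancy already reported.

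At stake is the completeness of a rare but important safety outcome. SAP 5.1.4 considers adverse events, including AESIs, recorded during the study period, so an unreported pregnancy would be missing from the safety results. No efficacy result is affected.

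**Working it through.** **Inputs from the documents**
- Planned end of treatment: Week 24 (core period) or Week 48 at most (extension).
- Post-treatment visit: 2 to 4 weeks after the last dose (6.1, 10.1.6).
- Post-dose contraception: at least 3 months (E 12), taken as 13 weeks or 91 days.
- Patients who stop treatment permanently: followed to the scheduled date of study completion (10.3.4).

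**Reproducing the plan's end-of-study dates**
- Core only: 24 + 2 = 26 and 24 + 4 = 28.
- With extension: 48 + 2 = 50 and 48 + 4 = 52.

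Both agree with section 6.2.2.

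**Share of the contraception period outside the window** = 1 − v/W, where v is the visit time and W the length of the period.

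| W | v = 2 weeks | v = 4 weeks |
|---|---|---|
| 13 weeks | 1 − 2/13 = 85% | 1 − 4/13 = 69% |
| 12 weeks (variant) | 1 − 2/12 = 83% | 1 − 4/12 = 67% |

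In days, with W = 91, the uncovered time is 91 − 28 = 63 to 91 − 14 = 77 days.

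**Who is affected.** If scheduled completion is Week 28, a core-period patient who stops treatment but stays in follow-up has all 13 weeks covered when her last dose is by Week 28 − 13 = 15. If it is Week 26, the limit is Week 13. Later stops are partly covered, and the shares above apply to completers and the latest stops.

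**Routes after the patient's end of study**

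| Provision | Covers a new, non-serious pregnancy? |
|---|---|
| 10.4.3, recording window | No, if it begins after the window closes |
| 10.4.4, post-study clause | No on its own terms: it needs an SAE judged caused by sarilumab |
| 10.4.5, reference to 10.4.4 | Unclear: it waives seriousness for notification but does not mention the post-study period or causality |
| 10.4.1.3, follow-up to outcome | Only once the pregnancy is known |
| Appendix A | Gives no procedure and no window |

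**Expected number** = women × annual failure rate × uncovered days / 365. The documents give no number of women of childbearing potential, so 20 to 30 is assumed. The failure rate is assumed at 1% to 7% per year; Table 2 gives below 1% for consistent and correct use and notes that typical use may differ.
- Low: 20 × 0.01 × 63/365 = 0.03.
- High: 30 × 0.07 × 77/365 = 0.44.
- 30 women at 1%: 30 × 0.01 × 77/365 = 0.06.

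**If the periods were aligned**, reporting would run to about Week 24 + 13 = 37 (core) or 48 + 13 = 61 (extension). That is 13 − 4 = 9 to 13 − 2 = 11 weeks later than now, with no uncovered share.

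**The case against.** The strongest reply is that these are two different provisions and do not contradict each other. E 12 sets a duration for contraception and nowhere says that reporting must match it. That is right. A reader might infer that the protocol itself declares 3 months to be the risk period for reporting, but it does not say so. The link is an inference from E 12 and Table 2, and the point is therefore an improvement to safety capture.

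Three other strong readings also go too far.
- **No post-study route exists at all.** Section 10.4.5 sends AESIs to 10.4.4 even when they are not serious, so a pregnancy arguably inherits the post-study clause. The causality condition would still stand and would rarely fit a pregnancy as such. The route is ambiguous and narrow, but not plainly absent.
- **A pregnancy begun before the last visit but found later is not reportable.** Section 10.4.3 sets no limit on the date of detection and expects that observation may continue after the last planned visit. Such a case is at most ambiguous.
- **The gap applies to every patient.** Section 10.3.4 covers many early discontinuers partly or fully.

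It is also fair to say that the pregnancy form listed in Table 1 and the consent form are not available here, and either might contain a window. For patients who move to commercial sarilumab, the last study dose is not the last exposure, so a window counted from it fits them less well. Finally, very few events are expected. These points limit the size of the concern, but none supplies a clear reporting duty in the protocol text.

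**Conclusion.** The concern holds for patients who complete treatment or stop late. For them, 69% to 85% of the protocol's own post-dose contraception period (67% to 83% if 3 months is read as 12 weeks) has no clear duty to report a new, non-serious pregnancy. These are shares of calendar time. Reading them as shares of pregnancies missed would need conceptions to be spread evenly over the period, which the documents cannot show.

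The absolute size is small, about 0.03 to 0.4 expected pregnancies, and rests on assumed numbers of women and failure rates. The point is worth acting on because the protocol made pregnancy immediately notifiable, a single missed case could be the only one, and the correction is cheap.

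**What to change.** Reconcile the pregnancy reporting period in Protocol 10.4.1.3, 10.4.3, 10.4.5, Table 1 and Appendix A with the post-dose contraception period already in E 12. State that a pregnancy the site learns of within that period is notified as an AESI regardless of seriousness or causality, on the existing pregnancy form and with follow-up to outcome. Put in Appendix A the collection procedure that its title announces. At the post-treatment visit, have site staff remind women of childbearing potential to tell the site if they become pregnant within that period. A line in SAP 5.1.4 should say that pregnancies notified after the last visit are included in the AESI presentation.

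No visit, test, dose or contraception rule changes. The cost is a few sentences of wording, a short reminder at an existing visit, and slight extra reporting work for sites.

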#### **10.4.4 Instructions for reporting serious adverse events**

In the case of occurrence of an SAE, the Investigator or any designees must immediately:

- ENTER (within 24 hours) the information related to the SAE in the appropriate screens of the eCRF; the system will automatically send a notification to the monitoring team after approval of the Investigator within the eCRF or after a standard delay.
- SEND (preferably by fax or e-mail) a photocopy of all examinations carried out and the dates on which these examinations were performed, to the representative of the monitoring team whose name, fax number, and email address appear on the clinical trial protocol. Care should be taken to ensure that the patient's identity is protected and the patient's identifiers in the clinical trial are properly mentioned on any copy of a source document provided to the Sponsor. For laboratory results, include the laboratory normal ranges.
- All further data updates should be recorded in the eCRF as appropriate, and further documentation as well as additional information (for laboratory data, concomitant medications, patient status, etc.) should be sent (by fax or e-mail) to the monitoring team within 24 hours of knowledge of the SAE. In addition, every effort should be made to further document any SAE that is fatal or life-threatening within a week (7 days) of the initial notification.

- A back-up plan (using a paper CRF process) is available and should be used when the eCRF system does not work.

Any SAE brought to the attention of the Investigator at any time after the end of the study for the patient and considered by him/her to be caused by the IMP with a reasonable possibility, should be reported to the monitoring team.

#### 10.4.5 Guidelines for reporting adverse events of special interest

For AESIs, the Sponsor must be informed immediately (ie, within 24 hours), as per SAE notification guidelines described in Section 10.4.4, even if not fulfilling a seriousness criterion, using the corresponding screens in the eCRF.

Instructions for AE reporting are summarized in Table 1.

#### 10.4.6 Guidelines for management of specific laboratory abnormalities

Recommended dose modifications in case of neutropenia, thrombocytopenia, or liver enzyme elevations are provided in the following tables.

Low Absolute Neutrophil Count	
Lab Value (cells x 10^9/L)	Recommendation
ANC greater than 1	Current dose of sarilumab should be maintained.
ANC 0.5-1	Treatment with sarilumab should be withheld until >1 x 10  /L. Sarilumab can then be resumed at 150 mg every 2 weeks and increased to 200 mg every 2 weeks as clinically appropriate.
ANC less than 0.5	Discontinue sarilumab.

Low Platelet Count	
Lab Value (cells x 10^3/μL)	Recommendation
50 to 100	Treatment with sarilumab should be withheld until >100 x 10  /μL. Sarilumab can then be resumed at 150 mg every 2 weeks and increased to 200 mg every 2 weeks as clinically appropriate.
Less than 50	If confirmed by repeat testing, discontinue sarilumab.

Liver Enzyme Abnormalities	
Lab Value	Recommendation
ALT >1 to ≤ 3 x ULN	Consider dose modification of concomitant DMARDs as clinically appropriate.

Liver Enzyme Abnormalities	
Lab Value	Recommendation
ALT >3 x and ≤5 x ULN	Treatment with sarilumab should be withheld until < 3 x ULN. Sarilumab can then be resumed at 150 mg every 2 weeks and increased to 200 mg every 2 weeks as clinically appropriate.
ALT >5 x ULN	Treatment with sarilumab should be discontinued.

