### **10.3.1 Temporary treatment discontinuation with investigational medicinal product**

Temporary treatment discontinuation decided by the Investigator corresponds to more than one sarilumab injection not administered to the patient. A temporary treatment discontinuation greater than 31 days has to be considered as permanent.

Temporary treatment discontinuation may be considered by the Investigator because of suspected or confirmed AEs. Re-initiation of treatment with the IMP will be done under close and appropriate clinical/and or laboratory monitoring once the Investigator will have considered according to his/her best medical judgment that the responsibility of the IMP in the occurrence of the concerned event was unlikely and if the selection criteria for the study are still met (refer to the Section 7).

For all temporary treatment discontinuations, duration must be recorded by the Investigator in the appropriate pages of the eCRF.

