### **10.3.3 List of criteria for permanent treatment discontinuation**

The patients may withdraw from treatment with the IMP if they decide to do so, at any time and irrespective of the reason, or this may be the Investigator's decision. All efforts should be made to document the reason(s) for treatment discontinuation and this should be documented in the eCRF.

Patients must discontinue sarilumab if they experience any of the following:

- Pregnancy in female patients
- Opportunistic infections (including but not limited to tuberculosis and disseminated herpes zoster) and serious infections
- Gastro-intestinal perforations or diverticulitis
- Neutropenia (ANC <500 cells/mm^3)
- Thrombocytopenia (platelet count <50,000 cells/mm^3)
- ALT or AST elevation of >5 times ULN
- Malignancies (with the exception of local basal or squamous cell carcinoma of the skin or carcinoma in situ of the cervix uteri that have been excised and cured)
- Signs/symptoms of anaphylaxis or hypersensitivity following SC administration of sarilumab
- Use of biologic DMARD other than sarilumab
- Any AEs, per Investigator's judgment, that may jeopardize the patient's safety.

Any abnormal laboratory value will be immediately rechecked for confirmation before deciding of permanent discontinuation of IMP treatment.

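### The liver table in Protocol 10.4.6 is keyed to ALT only and omits the permanent stop that 10.3.3 requires for AST above 5 x ULN

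*Protocol*

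**What the plan says.** Protocol 10.4.6 opens by covering liver enzymes in general: "Recommended dose modifications in case of neutropenia, thrombocytopenia, or liver enzyme elevations are provided in the following tables". All three rows of its liver table, however, are defined on ALT. The middle row, "ALT >3 x and ≤5 x ULN", reads "Treatment with sarilumab should be withheld until < 3 x ULN. Sarilumab can then be resumed at 150 mg every 2 weeks", with a later return to 200 mg as clinically appropriate. The last row calls for discontinuation when ALT exceeds 5 x ULN. AST appears nowhere in the table.

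Protocol 10.3.3 is a mandatory list: "Patients must discontinue sarilumab if they experience any of the following". One item is "ALT or AST elevation of >5 times ULN". The list closes with a recheck rule: "Any abnormal laboratory value will be immediately rechecked for confirmation before deciding of permanent discontinuation of IMP treatment".

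Protocol 10.3.1 governs temporary discontinuation, which "corresponds to more than one sarilumab injection not administered to the patient". It allows restart once the investigator considers that "the responsibility of the IMP in the occurrence of the concerned event was unlikely" and if the Section 7 selection criteria still hold. A temporary stop longer than 31 days counts as permanent.

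Sections 10.3.3 and 10.4.6 do not refer to each other. Section 8.1 sends the reader to 10.4.6 for the 150 mg syringes, and Section 10.6 sends the reader there for managing laboratory abnormalities. Neither mentions 10.3.3.

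**The concern.** A site handling raised transaminases is directed to 10.4.6. If AST is above 5 x ULN while ALT lies above 3 and up to 5 x ULN, the row that fits by ALT leads to a hold and then a restart at 150 mg. Section 10.3.3 requires the same patient to stop for good. A site working from the table alone could re-expose a patient whom the protocol says must not be re-exposed.

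A second question concerns restart. Section 10.3.1 makes restart depend on sarilumab being an unlikely cause. Section 10.4.6 provides for restart at 150 mg after neutropenia, thrombocytopenia or raised ALT, and sets no causality condition. Section 4.1.2 lists neutropenia, thrombocytopenia and raised transaminases among the drug's most frequent adverse reactions.

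**Working it through.** The plan states no figure on this point, so the check compares the rules themselves.

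**Stop rule.** Split each enzyme into four bands (x ULN): ≤1, >1 to 3, >3 to 5, >5. The ALT cut-points come from the 10.4.6 liver table and the >5 limit for either enzyme from 10.3.3. Applying the same bands to AST is a choice made here. That gives 4 x 4 = 16 combinations.

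| | AST ≤1 | AST >1 to 3 | AST >3 to 5 | AST >5 |
|---|---|---|---|---|
| ALT ≤1 | consistent | consistent | no hold specified | table silent; 10.3.3 stops |
| ALT >1 to 3 | consistent | consistent | no hold specified | table silent on sarilumab; 10.3.3 stops |
| ALT >3 to 5 | consistent | consistent | consistent | **table: hold, then 150 mg; 10.3.3: stop** |
| ALT >5 | consistent | consistent | consistent | consistent |

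- Opposing instructions: 1.
- Table gives no sarilumab action but 10.3.3 requires a stop: 2.
- AST >3 to 5 with no hold specified: 2.
- Consistent: 16 − 1 − 2 − 2 = 11.

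The stop required by 10.3.3 is therefore missing from the table in 1 + 2 = 3 combinations, all with AST >5 and ALT ≤5. The single opposing combination does not depend on how the lower AST bands are cut.

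**Restart rule.**

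1. Under 10.4.3, a laboratory abnormality that leads to a dose change or discontinuation is recorded as an AE, so a laboratory hold can fall under 10.3.1.
2. It does so only when more than one injection is missed. A hold of one injection is outside 10.3.1.
3. The start of the 31-day count is not defined. Assume that it runs from the first missed dose and that dosing resumes on the two-weekly schedule. Two missed doses then give 2 x 14 = 28 days, within the limit. Three give 3 x 14 = 42 days, beyond it. On that assumption the question concerns holds of two missed injections.
4. For those holds, 10.3.1 read literally bars restart whenever sarilumab is a likely cause, while 10.4.6 allows restart at 150 mg once the value recovers.
5. The restart level in the middle liver row belongs to an ALT row. No AST level for restart is given in 10.4.6.

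**The case against.** The strongest reply is that the two sections do not impose opposing duties. Section 10.3.3 says *must*; 10.4.6 offers recommendations and says sarilumab *can* be resumed. A permission does not defeat a mandatory stop, and a site that stops permanently breaches nothing in 10.4.6. This largely stands: precedence is implied, and harm requires a site to overlook the list in 10.3.3. It does not remove the point, because the routes into the dosing rules (8.1 and 10.6) lead to the table that lacks the AST stop.

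The sarilumab product characteristics are listed as an appendix, and Section 15 makes appendices part of the protocol, but their text is not available here. They may settle precedence. ALT-only holds may also be intended: 10.4.1.2 and the combined ALT and bilirubin row of SAP Appendix J use ALT alone. The missing hold for AST >3 to 5 x ULN is therefore a query, not a shown error.

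A reader might infer a firm clash of restart thresholds, because 10.3.1 requires selection criteria to be still met and E 20 excludes ALT or AST >1.5 x ULN, ANC <2 x 10^9/L and platelets <150 x 10^3/μL, whereas 10.4.6 allows restart at ALT <3 x ULN, ANC >1 and platelets >100. The documents do not establish this. E 20 is tied to the Screening or Baseline visit. Other criteria carry similar anchors that must be kept: without them, a responder with DAS28-ESR ≤3.2 would fail I 02 and every treated patient would fail E 03. Section 10.4.6 itself maintains the dose at any ANC above 1 and names no sarilumab hold at ALT up to 3 x ULN. Applying E 20 at restart is one possible reading only.

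A reader might also infer an effect on the primary analysis, since SAP 6.4 carries forward the last RAID value after discontinuation for an AE. That rule applies to any such discontinuation, and nothing shows that this ambiguity would change the result.

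**Conclusion.** The point holds as a minor safety clarification. The 10.4.6 liver table omits the AST stop that 10.3.3 already requires. In one of 16 band combinations it recommends a hold and restart for a patient who must stop, and in two more it gives no sarilumab action. These are counts of rules; the documents do not allow the number of patients to be estimated. On an ordinary reading 10.3.3 prevails, so the defect is a table that misleads when read alone, not two equally binding instructions.

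The restart question is secondary and goes to the sponsor as a query. It rests on laboratory holds falling under 10.3.1 and applies only after more than one missed injection. If 10.3.1 governs those holds, its causality condition would probably block many of the 150 mg restarts that 10.4.6 provides for. No statistical figure in the plan changes.

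**What to change.** Replace the last row of the 10.4.6 liver table with: *ALT or AST >5 x ULN (confirmed on recheck): discontinue permanently per 10.3.3; this overrides the hold-and-resume row.* This adds no test, because AST is already drawn with ALT, and changes no threshold, because 10.3.3 already sets it. The cost is one table row in a protocol amendment.

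Put two questions to the sponsor's clinical and safety team:

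- Which section governs restart after a laboratory hold of more than one injection, 10.3.1 or 10.4.6, and does the causality condition apply?
- What AST level allows restart, and are ALT-only holds intended?

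Do not simply declare that the 10.4.6 thresholds replace the 10.3.1 conditions. If E 20 is read as applying at restart, that would remove the only AST limit there. If the sponsor adds AST to the hold row, a few more temporary holds may follow, and any that exceed 31 days become permanent.
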